The purpose of this study was to build upon our community-based participatory research (CBPR) partnerships with the [tribal name] tribal community to culturally adapt an evidence-based, indicated PEI program for universal delivery with 8-12-year-olds living on the [tribal name] Reservation using a systemic, theory- and culturally-grounded qualitative approach. In addition, we will use a mixed methods approach to evaluate the feasibility of delivering the adapted PEI in two tribe-serving schools and estimated effect sizes of changes in anxiety and depression from pre- to post-intervention using single-group design (i.e., no control group). We also aimed to determine the extent to which the program was acceptable and enjoyable for [tribal name] youth.

Research Design

Our study involved two major phases:

- 1) a qualitative phase, which included collaboration between the CAB and research team that resulted in a conceptual framework for cultural adaption of the PEI program, gathering suggestions for cultural adaptations and to improve the PEI program from focus groups with key adult stakeholders in the [tribal name] community (Elders, parents, teachers, and mental health specialists) and youth stakeholders, and the CAB making cultural adaptions to the PEI program based on the focus group data.
- 2) a clinical trial phase, which included delivery of the adapted intervention in two tribal serving schools for the [tribal community name] Reservation using a pre-post, single group design (i.e., no control group). We evaluated feasibility and acceptability using youth and provider self-report data and estimated the effect sizes of changes in youth anxiety and depressive disorder symptoms using youth and teacher reports. In addition, we gathered survey data on youth resilience, anxiety control beliefs, and rumination.

Cultural Adaptation of the PEI Program (Phase 1)

Development of Conceptual Framework and Review of the PEI program (Step 1)

In Year 1, the 8-10 member CAB (Elders, parents, teachers, mental health professionals, cultural experts) and research team met once a month and engaged in several activities throughout Step 1 described in this section and Step 3 described in a later section. All CAB members completed a

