At the end of Year 2, the CAB and research team met to review all grouped suggestions gathered from the WGs and FGs. The CAB identified and integrated modifications or additions to our conceptual framework if needed based on the FG feedback. Next, the CAB reviewed the content, format, and learning objectives of each of the six PEI program modules and training protocol within the context of this finalized conceptual model. Specifically, the CAB identified the type of change needed (e.g., content, language, learning strategy), amount of change required (no change, small change, moderate change, large change), and barriers (timeline/budget). The CAB decided on the importance of the change (essential or non-essential), made final decisions on adaptations, and the physical adaptations of the PEI program materials were made by the developers of PEI as requested by the CAB.

Adapted PEI Program Intervention Evaluation (Phase 2; Clinical Trial)

In Year 3, The CAB worked with the research team to culturally adapt the intervention and identified two school counselors (i.e., an American Indian tribal member and a white non-tribal member) to provide it in the schools. Both providers completed the modified PEI program training based on CAB decisions for adaptation and the CITI Training (through Montana State University-Bozeman) before working with youth in the school. They also completed a background check for each school. Providers recorded youth attendance, dropout of the intervention, and completed the Brief Reactions Form for after each session.

In Year 3, we recruited 28 Native youth ages 8-12 years-old from the [two tribal serving school names] (15 youth per school) to participate in the adapted PEI program. The adapted PEI program was delivered to a group of 3-5 youths at one time with three groups participating in each school. Written informed consent was obtained from the parents or legal guardians before youth participated in the intervention or complete pre- and post-survey assessments. Youth participants also provided written assent before completing the pre-intervention and post-intervention surveys or participating in the adapted PEI program.

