The Child and Youth Resilience Measure (CYRM).^{39,40} The CYRM is a 36-item measure (10 items constructed by the CAB and used in our previous pilot study; Scott, [name], Small, & McCullen, under review) that assesses global and tribal specific resilience across a number of areas including: personal skills, peer support, social skills, physical and psychological caregiving, spiritual, educational, and cultural. We asked the children to indicate to what extent each statement described them (e.g., “Getting an education is important to me,” “I try to finish activities that I start,” and “I feel supported by my friends”) on a three-point scale of “No,” “Sometimes,” and “Yes.” Higher scores reflect greater resiliency for each of the sub-domains (e.g., peer support, spiritual).

*Anxiety Control Questionnaire for Children- Short Form (ACQ-C Short Form).*⁴¹ The ACQ-C Short Form is a 10-item developmentally modified version of the ACQ and assesses children’s control beliefs over anxiety-related “external” threats (e.g., fear-producing objects, events, and situations) and/or “internal” emotional or bodily reactions (e.g., flushed face). The items on the ACQ-C were changed to be developmentally appropriate and include such questions as “I can usually stop my anxiety from being seen by other people” and “I can usually stop thinking about things that make me nervous or afraid if I try.” We asked children to rate how much they agreed with the item on a 6-point Likert-type scale consisting of: 0 (Strongly Disagree), 1 (Moderately Disagree), 2 (Slightly Disagree), 3 (Slightly Agree), 4 (Moderately Agree) or 5 (Strongly Agree).

Child Response Styles Questionnaire – Rumination Subscale (CRSQ).^{42,43} The CRSQ – Rumination Subscale is 12 items that assess children’s regulation of sadness using rumination. We asked children to rate how often they engage in rumination when feeling sad (e.g., “When I am sad, I think about how alone I feel.” on a 4-point scale consisting of “Almost Never,” “Sometimes,” “Often,” and “Almost Always. Higher scores represent greater use of rumination when feeling sad.

Teacher Assessments. The following two questionnaires were completed by each child’s homeroom teacher. The CAB previously reviewed and approved the following instruments as being culturally appropriate (minor changes were made to existing measures) for our previous study with 71 Native 8-13-years-old at the [tribal school name] School. Each measure showed

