We also will conduct individual interviews with 4 parents, 4 3rd-6th grade homeroom teachers, and the two providers of youth intervention participants. Youth will participate in the focus group on the last day of the intervention and parent/teacher/youth interviews will happen within a month of the last day of the intervention. Focus groups and interviews will be audio recorded.

Post-Intervention Acceptability Focus Group and Interview Procedure. We followed the same aforementioned general procedures for the focus groups. [name] and the project manager asked youth to describe what they liked about the adapted PEI program, which they thought was most useful, and whether it was appropriate for AI youth. They also asked for suggested improvements to content, material, and learning strategies. AI youth received a \$20 gift card for their participation.

Youth Post-Adaptation Usability Survey. Youth completed the identical usability survey³⁶ from the pre-adaptation phase at the end of each session. It assessed likability, acceptability, enjoyable, ease of learning and using skills, credibility, motivational appeal, perceived impact, and cultural appropriateness.

References

1. Evans-Campbell T. Historical trauma in American Indian/Native Alaska communities: A multilevel framework for exploring impacts on individuals, families, and communities. *Journal of interpersonal violence*. 2008;23(3):316-338.
2. Brown-Rice K. Examining the Theory of Historical Trauma Among Native Americans. *Professional Counselor*. 2013;3(3).

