- B. Confidentiality. We will ensure the steps necessary to ensure confidentiality of the work and focus group discussions and audio recording data. [name] (Project Manager) will inform participants that she cannot guarantee confidentiality of group discussions. However, she will explain to all work/focus groups members the importance of respecting others and maintaining confidentiality of the group discussions. All digitally recorded data gathered from the work and focus groups with tribal community stakeholders (Elders, parents/legal guardians, counselors) and youth will be kept on the Montana State University's Knox password-protected server as an encrypted electronic file. The server is maintained by the university. We will use unique ID code as the file name, which will include the school code, session number, and the recording date. The name of the participant or other identifying information will not be used in the file name. Only trained research staff will have permission to access the Knox folder and review the audio recordings for transcription and analysis.

We also will take the necessary steps to ensure the confidentiality of the survey data. Specifically, we will assign a unique ID number for each youth prior to the administration

of the pre-intervention survey. This unique ID number will only be included with the youth's name on a Master List and will be used as the ID number in the complete deidentified aggregate data file used for study analyses. In addition, only the unique ID number will be present on the surveys. The Master List will contain the unique ID number and the associated youth's name. The Master List with identifying information (i.e., names) and associated unique ID numbers will be kept [name] encrypted and password-protected electronic file on the Montana State University's Knox password-protected server, which is maintained by MSU. [name] will be the only person to have access to the Master List (paper and electronic copy). Additional research staff will not have access to the Master List. The data will only include the unique ID code and no other identifying information.

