Study Aim 2: Evaluate the feasibility and acceptability of the culturally adapted PEI program. We calculated the frequency of youth attendance rates across sessions, dropout rates, and survey response rates. We also created tabular summaries of the Likert scale ratings from the usability survey and proportion of respondents who rated each module or all modules on average as 2 or 3. A module or the entire program was successfully adapted if at least 80% of youth rated it as a 2 or 3 on the Likert scale for acceptability and enjoyability.

Study Aim 3. Estimate effect size changes in anxiety and depressive symptoms in [tribal name] youth. Primary outcomes of interest for a future efficacy trial will be changes in the RCADS-S scales. For each scale, we computed the change in the scale score from baseline to post-intervention (post – pre) and computed unadjusted averages and standard deviations. A one-sample t-test of the changes in any response scale will have 80% power to detect a standardized effect size (Cohen's d) of at least 0.53, and 90% power to detect an effect size of at least 0.61. We will also obtain adjusted estimates using mixed effects linear regression models of post-test score on pre-test score with demographic factors and random effects for school and intervention group nested within school. This will allow us to estimate intra-class correlations for intervention group and schools, which will be required for sample size estimation in a full efficacy trial.

INSTITUTIONAL REVIEW BOARD AMENDMENTS

The following pages (not numbered, but in order of date) contain tribal college IRB amendments that were submitted and approved throughout the study period.

February 9, 2021

Dear [tribal college] IRB,

We are requesting a minor modification for the approved study titled, "A Native Path to Courage." We have outlined the modification below.

- 1) We plan on using a professional online transcription service (Rev.com) to transcribe work and focus group data. The company uses state-of-the-art encryption procedures for audio files to be uploaded and all professional transcribers are required to sign nondisclosure and confidentiality agreements (<https://www.rev.com/enterprise/security>). In addition, we can request for all audio files to be removed from their servers after transcription is complete. We will remove names from the transcription documents upon receipt. Only first names are mentioned in the audio recordings.

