Montana State University
[contact]
[contact]

[name]
[name]
[name]
www.montana.edu/wwwpy

[contact]
[contact]

February 16, 2024

Dear [tribal college] IRB,

We are requesting a minor modifications for the approved studied titled, "A Native Path to Courage." We have outlined the modifications below and attached a modified, track-changed protocol for review.

- 1) We have revised the study protocol in the following ways (see attached application amendments):
 - a. The intervention will be offered as part of an after-school program instead of during regular school hours.
 - b. We will collect pre-intervention survey data 1 week before the intervention begins, instead of 2 weeks.
 - c. We will conduct the child focus groups on the last day of the intervention, instead of 2 weeks after the intervention ends.
 - d. The provider will lead the focus group and [name] will assist the provider.
 - e. [Project manager name] will say a prayer before the focus group, as it may be difficult to have an Elder present for after-school activities.
- 2) We have revised the caregiver consent forms and child assent forms to reflect these changes to the protocol.

Sincerely,

[name].
Associate Professor
Department of Psychology
Montana State University
[contact]
[contact]

[name]
[name]
[name]
www.montana.edu/wwwpy

[contact]
[contact]

March 23, 2024

Dear [tribal college] IRB,

We are requesting a minor modifications for the approved studied titled, "A Native Path to Courage." We have outlined the modifications below and attached a modified, track-changed protocol for review.

- 1) The original application alluded to each homeroom teacher's assessment of youth anxiety and depression. However, the application did not explicitly state the specific measure to be administered or provided the IRB with the actual measure which is the Revised Child Anxiety and Depression Scale (RCADS). The RCADS-Teacher Version is identical to the approved youth version with minor wording changes (e.g., "I" to "My student." Please see attached RCADS-Teacher Version measure which was previously used and approved by the [tribal college] IRB for our initial study at the [tribal school name].
- 2) We request that each homeroom teacher complete a four-item demographic form asking for their age and gender identity, race, and ethnicity.

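### Does the lack of a homeroom-teacher rater effect undermine the planned analysis of teacher-reported symptom change?

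*Combined protocol and SAP*

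**What the plan says.** The Research Design section says that effect sizes are estimated for anxiety and depression "symptoms using youth and teacher reports". Under Teacher Assessments, "The following two questionnaires were completed by each child" is followed by the rater's role: the homeroom teacher. The teacher RCADS has 25 items.

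Under Study Aim 3 the SAP takes post minus pre on each RCADS scale and gives the unadjusted mean and SD. It adds a power statement for "A one-sample t-test of the changes in any response scale": 80% at d = 0.53 and 90% at d = 0.61. It then plans a mixed model of post-test on pre-test with demographic factors and "random effects for school and intervention group nested within school". The group and school ICCs from that model are meant to help size a later efficacy trial.

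In the Phase 2 section the program is "delivered to a group of 3-5 youths at one time with three groups participating in each school", with 28 youth recruited. The Confidentiality section of the Data and Safety Monitoring Plan says "we will assign a unique ID number for each youth" and mentions no code for teachers. The March 23, 2024 amendment letter states "We request that each homeroom teacher complete a four-item demographic form". The number of rating teachers is not given; "4 3rd-6th grade homeroom teachers" is an interview target.

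**The concern.** A different rater for every child would take 28 homerooms, so shared raters are very likely. The SAP nevertheless treats teacher report like self-report. If a teacher's expectations shift over the program, all of that teacher's children shift together, and an analysis that takes children as independent is too precise.

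Two things would be at stake. Teacher report is the only symptom outcome not given by the child in a study without controls, so false precision there could mislead. And rater variance could enter the group or school ICC and carry over into the efficacy trial's sample size. Without a teacher code, a later analyst might be unable to separate these sources.

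**Working it through.** **The plan's own figure.** Noncentral t, two-sided 5% (assumed; the SAP states no alpha), independent children, noncentrality d√n.

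| n | d = 0.53 | d = 0.61 |
|---|---|---|
| 30 (15 per school) | 80.1% | 89.8% |
| 28 (recruited) | 77.1% | 87.5% |

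The stated power reproduces at n = 30, with no allowance for clustering.

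**Inputs the documents do not give.** Number of raters, children per rater, teacher-by-group mapping and teacher ICC of change are all assumed. The base case is eight raters: one homeroom per grade 3 to 6 at each school, with 4, 4, 3 and 3 children per school. Stable leniency cancels in change scores, so small ICCs belong in the range.

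**Plain t-test on 28 changes.**
- Design effect: DE = 1 + ICC × (Σm²/n − 1). Here Σm² = 2 × (16 + 16 + 9 + 9) = 100 and 100/28 = 3.571, so DE = 1 + 2.571 × ICC.
- Expected sample variance, in units of the true variance: E = 1 − (DE − 1)/27.
- Actual error: P(|t₂₇| > 2.052/√(DE/E)).

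| ICC | DE | Effective n = 28/DE | Actual error, nominal 5% |
|---|---|---|---|
| 0.02 | 1.051 | 26.6 | 5.6% |
| 0.05 | 1.129 | 24.8 | 6.5% |
| 0.10 | 1.257 | 22.3 | 8.0% |
| 0.20 | 1.514 | 18.5 | 11.0% |

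Uneven classes (6, 4, 3, 1 per school) give 9.0% and 13.0% at ICC 0.1 and 0.2. Fourteen raters with two children each give 6.1% and 7.3%. Four raters with seven each give 12.0% and 18.8%, but nothing in the documents points to four.

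**Planned school-plus-group model, no teacher term.** In simulation (3,000 data sets per setting, 28 children, two schools, six groups):
- Change on centred pre-test with 26 residual df: 3.1% with no clustering; 5.6% and 7.3% with eight raters at ICC 0.1 and 0.2; 6.0% if teachers coincide with groups (ICC 0.2).
- A version with pre-test and two demographic covariates, teacher ICC up to 0.3: with eight raters, 2.9% to 6.0% using Satterthwaite df and 5.0% to 10.0% using Wald z; with four raters, 4.9% to 9.5% and 8.2% to 16.7%.

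The model is partly protected because teachers sit within schools, so the school and group terms absorb part of the shared variation.

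**ICCs (true school and group ICC zero, teacher ICC 0.2).** With eight raters crossing groups, the mean estimated school ICC moves from 0.029 (SD 0.067) to 0.053 (SD 0.102), with median 0 both times; the group ICC stays at 0.047. If teachers coincide with groups, the mean group ICC is 0.16 to 0.18, against about 0.05 with no clustering.

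**What a remedy would buy.** Adding a teacher random effect lowers the mean school ICC from 0.053 to 0.043, and does nothing if teachers coincide with groups. Teacher-clustered CR2 intervals hold 5% when the teacher is the only source of clustering. They have about 6.8 df, are 1.12 times the plain width even with no rater clustering (1.26 and 1.39 times at ICC 0.1 and 0.2), and ignore clustering by group.

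**The case for a change.** The best case for acting is that the fix is cheap and that some information, once lost, cannot be recovered. If teachers coincide with groups, a group ICC of 0.16 to 0.18 instead of about 0.05 would matter to an efficacy trial: with 28/6 = 4.67 children per group the design effect goes from about 1 + 3.67 × 0.05 = 1.18 to about 1 + 3.67 × 0.16 = 1.59. A rater code and a table of teachers by group would at least show whether that situation arose. The SAP also names no degrees-of-freedom method, so the reassuring error rates for the mixed model are not guaranteed.

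Part of this stands. Reporting the number of raters and children per rater would be good practice, and near-nominal behaviour of the model depends on about eight or more raters, a modest ICC and small-sample df. But where teachers coincide with groups, a teacher term cannot separate the two. The SAP's per-scale analysis also yields child-report ICCs, which contain no teacher-rater variance and can be set beside the teacher-report ones. In the base case the teacher is identified by school and grade, and the youth demographics already record grade. Silence about a teacher code is weak evidence that none exists, since the teacher forms and the modified IRB application are attachments not reproduced here.

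**Conclusion.** The gap is genuine, but it does not call for a change. For unadjusted change the SAP commits to means and SDs; the t-test appears only in a power sentence, and no alpha, p-value rule or interval is laid down. Rater clustering leaves the mean unbiased. The excess error of a plain t-test, 5.6% to 11.0% with eight raters at ICC 0.02 to 0.2, is therefore hypothetical twice over: in its inputs, and in whether such a test is reported at all.

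The planned mixed model is little affected under the base case with small-sample df. With Wald z or only four to six raters it can be clearly above 5%, but the documents do not establish either condition. Two schools cannot give a usable school ICC with or without a rater term, and a third variance component at n = 28 is a debatable gain. In a single-arm feasibility study whose stated aim is estimation, analysts can sensibly report rater counts and read teacher-report ICCs with caution, without amending the plan.

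### Two schools and six groups cannot supply the school ICC that the SAP promises for sizing the efficacy trial, and give only a very imprecise group ICC

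*Combined protocol and SAP*

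**What the plan says.** The SAP for Phase 2, Study Aim 3, plans adjusted estimates from a linear mixed model of post-test on pre-test score, with demographic factors and "random effects for school and intervention group nested within school". It then gives the model a second purpose: "This will allow us to estimate intra-class correlations for intervention group and schools, which will be required for sample size estimation" in the later trial.

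The cluster counts are in the protocol. Research Design describes "delivery of the adapted intervention in two tribal serving schools". The Phase 2 evaluation section says "we recruited 28 Native youth ages 8-12 years-old", with the program "delivered to a group of 3-5 youths at one time" and "with three groups participating in each school". The same section says that the board and research team "identified two school counselors" as providers, without saying who taught where.

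The documents give no expected ICC, no interval for either ICC, no rule for a variance component estimated at zero, and no external source of ICC values.

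**The concern.** How well an ICC is estimated depends mainly on the number of clusters at that level, and only secondarily on the number of youth. With two schools, the between-school variance rests on a single contrast. Software will return a number for it, but that number hardly separates no clustering from substantial clustering. The group ICC is a separate and lesser problem: six groups give an estimate, but a very loose one.

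The SAP presents both as required inputs to the efficacy trial. A bare point estimate of either, carried forward, could make that trial too small or too large. If each counselor served one school, the school term would also contain any provider difference. The documents do not settle this, and the point does not depend on it.

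**Working it through.** **No stated ICC figure to reproduce.** The only computed figures in the SAP are the power values for the one-sample t-test. They reproduce at n = 30, two-sided 5% (assumed): 80.1% at d = 0.53 and 89.8% at d = 0.61. They have no bearing on the ICCs.

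**Inputs from the documents.** 2 schools; 3 groups of 3-5 youth per school; 28 youth recruited.

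**Assumed.** Groups of 5, 5 and 4 in each school (total 28); true ICCs between 0 and 0.20.

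**Degrees of freedom.** Between schools: 2 − 1 = 1. Groups within schools: 2 × (3 − 1) = 4. Within groups, before covariates: 28 − 6 = 22.

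**School level.** The 95% limits for a mean square on 1 df are 1/χ²(0.975; 1) = 0.20 and 1/χ²(0.025; 1) = 1018 times its estimate. An approximate interval for the school ICC therefore runs from 0 to about 0.99 for every true value tried (0.01 to 0.10).

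**Simulation of the planned model.** REML, 1,000 replicates per setting; post-score variance given pre-score = 1; pre-post correlation 0.6; pre-score in the model. The 2.5th percentile of every estimate is 0.

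| True group ICC | True school ICC | School estimate zero | School 97.5th pct | Group estimate zero | Group 97.5th pct |
|---|---|---|---|---|---|
| 0.05 | 0 | 68.5% | 0.286 | 53.2% | 0.365 |
| 0.05 | 0.02 | 63.9% | 0.323 | 51.3% | 0.391 |
| 0.10 | 0.05 | 59.1% | 0.408 | 40.7% | 0.425 |
| 0.05 | 0.10 | 53.0% | 0.504 | 48.9% | 0.389 |
| 0.05 | 0.20 | 38.4% | 0.651 | 49.4% | 0.372 |
| 0.10 | 0.20 | 38.8% | 0.659 | 38.0% | 0.423 |

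With age and sex added as demographic factors, for true school ICCs of 0.02 to 0.20, the school estimate is zero in 41-62% of fits with a 97.5th percentile of 0.38-0.65. The group estimate is zero in 39-55%, with a 97.5th percentile of 0.35-0.44. A nested-ANOVA simulation by a different route (200,000 runs per setting) gives similar school figures: zero in 69% at a true value of 0 and in 40-41% at 0.20.

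**Group level, F interval on (4, 22) df.** This concerns group variance over group plus residual variance.

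- Adjusted group size: each school has 5² + 5² + 4² = 66 and 14 youth, so n₀ = (28 − 2 × 66/14)/4 = 4.64.
- Observed ICC 0.05: F = 1 + 4.64 × 0.05/0.95 = 1.244.
- F quantiles: 3.440 (97.5%) and 0.1172 (2.5%).
- Lower limit: 1.244/3.440 = 0.362, and (0.362 − 1)/(0.362 − 1 + 4.64) = −0.16, taken as 0.
- Upper limit: 1.244/0.1172 = 10.62, and (10.62 − 1)/(10.62 − 1 + 4.64) = 0.67.
- Observed ICC 0 (F = 1): upper limit 0.62.

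**What this means for sample size.** The design effect is 1 + (m − 1) × ICC.

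- Groups of 5, ICC 0.05: 1 + 4 × 0.05 = 1.2. Over the interval 0 to 0.674 it runs from 1.0 to 1 + 4 × 0.674 = 3.7.
- Illustration only: if the efficacy trial randomised schools with 15 youth each and the true school ICC were 0.05, the design effect would be 1 + 14 × 0.05 = 1.7. A zero estimate would put it at 1.0, which is 1 − 1/1.7 = 41% too few participants.

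**The case against.** The strongest reply is that imprecision is normal in a pilot and that the harm lies outside this trial. The SAP says ICCs will be needed for sizing; it does not say that these point estimates will be used alone or that external values will be ignored. Estimating them is secondary to the effect-size aim. This stands as far as it goes: mis-sizing follows only if a later team relies on a bare estimate. But the SAP names these ICCs as an output with a stated use, and plans neither an interval nor another source.

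The 41% figure rests on three assumptions (schools randomised, 15 youth per school, true ICC 0.05). If youth were randomised within schools, the school ICC would not inflate the sample in that way. It shows a possible size and is not a consequence of the plan.

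The F interval is approximate: the groups are unequal and the planned model has covariates. Allowing 19 residual df moves the upper limit only from 0.674 to 0.676. It also leaves school variance out of the denominator, whereas the simulation includes it, so the two group ICCs are not quite the same quantity. Neither matter changes the conclusion.

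**Conclusion.** The concern holds. The SAP gives the design a property it does not have. With 1 df between schools, the school ICC cannot be usefully estimated: for true values of 0.02 to 0.20, the estimate is exactly zero in 38-64% of simulated fits, and the upper end of the central 95% of estimates is 0.32-0.66. The group ICC, on 4 df, can be estimated but very imprecisely: for true values of 0.05 to 0.10, it is zero in 38-53% of fits, and an observed 0.05 is compatible with anything from 0 to about 0.67.

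These figures rest on assumed true ICCs, an assumed split of the 28 youth into groups, and full follow-up. The conclusion is the same across the range tried, and dropout would make precision worse. The consequence is limited to planning of the efficacy trial, so this should be fixed but does not threaten the present results.

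**What to change.** In Study Aim 3 of the SAP:

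- Remove the statement that a school ICC from this study will be an input to the efficacy-trial sample size.
- Report the group ICC with a 95% interval and label it exploratory.
- State that the efficacy trial will be sized over a range of ICCs from external or pooled school data, with this trial's interval used only as a check.

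The planned model can stay. Treating school as a fixed effect is optional: it limits inference to these two schools and does not make the group ICC more precise.

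The cost is SAP wording and one confidence interval, with no new data and no change of model. The sponsor gives up the school ICC as a planning input and must find external or pooled values.
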